8.5.4. COMPLIANCE TO STUDY VISITS

Depending on patient general health status, visits to the Investigator site may occur after enrolment at interval of 2 or 4 weeks. Visits schedule can be adapted according to Investigator-patients agreement, as presented in Tables 1 and 2.

Table 1. Study Visits with Allowed and Suggested Time Intervals – First Case Scenario – Enrolment at Visit 1

Visit Number	Time Interval (Days)	
	Suggested	Allowed
Visit 1 (Screening and Enrolment)	Day 1	
Intermediate Phone Call	Day 15	Day 13 to 17
Optional intermediate evaluation Visit	Day 15	Day 13 to 19
Visit 2	Day 29	Day 29 to 43
Phone Call	Visit 2 Day + 7 days	Visit 2 Day + 14 days

Table 2. Study Visits if with Allowed and Suggested Time Intervals – Second Case Scenario – Enrolment at Visit 1A

Visit Number	Time Interval (Days)	
	Suggested	Allowed
Visit 1A (Screening and Enrolment)	Day 1	
Visit 1B	Day 8	Day 8 to 29
Intermediate Phone Call	Visit 1B Day + 14 days	Visit 1B Day + 12 to 16 days
Optional intermediate evaluation Visit	Visit 1B Day + 14 days	Visit 1B Day + 12 to 18 days
Visit 2	Visit 1B Day + 28 days	Visit 1B day + 28 to 42 days
Phone Call	Visit 2 Day + 7 days	Visit 2 Day + 14 days

8.5.5. COMPLIANCE TO DIARY COMPLETION

Compliance to diary completion (APS, WPS, rescue analgesic treatment recording) will be checked by Investigator at each visit at Investigator site.

9. EXPLORATORY ASSESSMENTS

Use of potentially available archived tumor tissue block and/or aliquot of standard safety laboratory blood sample for genotyping purposes are optional in this study.

Since genetic variation may influence a patient's response to therapy and may impact the mechanism of action and fate of drugs (absorption, distribution, metabolism, and excretion), metabolism enzyme, transporter polymorphisms, expression of proteins, disease etiology and/or molecular subtype of the disease being treated, pharmacogenetic may be explored in this study.

If the patient agrees to and signs the specific genotyping ICD, an aliquot of standard safety laboratory blood sample will be collected for potential pharmacogenetic analysis and archived tumor tissue block available at the Investigator site may be re-analyzed for genetic purposes.

Genetic material derived from those samples may be tested in any circumstances of an unexpected observation of unusual response. These analyses of genetic variants may evaluate a genetic association with response. These investigations may be limited to a focused candidate gene study or, if appropriate, genome wide association studies may be performed to identify regions of the genome associated with the variability observed. Samples will only be used for investigations related to the pain disease and drug or class of drugs under study in the context of this clinical study. They will not be used for broad exploratory genetic analysis.

Procedures for management of blood sample aliquot and retrieved tissue will be specified in a separate document.

The samples will be identified by the patient number (coded) and may be stored for up to 15 years after study last patient visit at a facility selected by the Sponsor. Any remaining sample stored for this study at that time will be destroyed. The blood and tissue sample and any data generated from it can only be linked back to the patient by Investigator site personnel. Pharmacogenetic data will not be provided to the Investigator unless required.

Patients will not be notified with regard to genotyping results unless required by local regulations.

10. STATISTICAL ANALYSES

10.1. DATA ANALYSIS PLANS

10.1.1. GENERAL CONSIDERATIONS

For all enrolled patients, pharmacodynamic analyses will be conducted on the full analysis set.

All tests of treatment effects will be conducted at a two-sided alpha level of 0.05, unless otherwise stated.

Additional exploratory analyses of the data will be conducted as deemed appropriate.

Detailed plan for the statistical methods for the safety and other variables will be provided in a Statistical Analysis Plan (SAP). This plan will be finalized prior to database lock.

10.1.1.1. Analysis Populations

Statistical analysis and data tabulation will be performed using the full patient population unless specified otherwise.

The patients constitute data vectors of potentially all data sources:

- CRF entries,
- Item-level entries from personality questionnaires
- Facet-level summaries from personality questionnaires
- Meta-level summaries from personality questionnaires
- Diary entries
- Meta-level summaries from diary
- Pain evaluations

At any time during the statistical analyses, a subset of those vector entries (thus reducing the population to some of these input features only) might be considered.

In some exploratory analyses, new populations might also be defined, for example based on sub-groups of patients showing similar pain evolution throughout the study.

A special set of features – the target features – characterize the analgesic efficacy and are defined as follows:

- APS difference with respect to baseline (primary endpoint)
- WPS difference with respect to baseline (secondary endpoints)
- BPI difference with respect to baseline (secondary endpoints)
- IGAC difference with respect to baseline (secondary endpoints)
- PGAC difference with respect to baseline (secondary endpoints)
- QLQ-C30 with respect to baseline (secondary endpoints)
- CPAs difference with respect to baseline (secondary endpoints)

10.1.1.2. General Statistical Procedures

The statistical analyses will be divided into four main parts (P1 to P4): descriptive, univariate, multivariate and exploratory. The descriptive part intends to describe the data by generating a set of statistical summaries of each patient-vector entry. The univariate analysis will investigate the link between each patient-vector entry and the treatment response (as described by the pain evolution). All the statistical procedures will further be described in a dedicated SAP.

P1 - Data Description

P11: Data pre-processing and summary.

Classical statistical information will be computed for each input feature (mean, median, standard deviation). A log-transform will be applied to some features, when appropriate.

P12: Missing values management.

The number of missing values will be reported for each feature. In subsequent analyses, value imputation might be performed if needed. Such cases will be documented.

P13: Outlier detection.

Population outliers will be detected through a Principal Component Analysis (PCA) visualization. Outliers might be removed for at least parts of the further analyses. Such cases will be documented.

P2 - Univariate Analysis

P21: Features Impact Assessment.

The correlation between each feature and the treatment response in terms of target feature will be assessed.

For each test performed in P2, if a non-conclusive p-value is obtained and when possible, an estimation of the required sample size will be performed based on the study data.

P3 - Multivariate Analysis

The aims of the multivariate analysis are i) to explore links between features (including all input and target features), ii) to predict target features based on input features, iii) to identify most important input features for this predictive task.

P4 - Exploratory Analysis

P41 - New populations identification.

We identify subgroups of patients with intra-group similar pain evolution curves, and inter-group different pain evolution curves. We define new “class labels” accordingly. If coherent profiles are found, we might consider applying a modeling procedure similar to P3.

P42 – Genetic data exploitation.

In case the genetic material from patients is used, similar experiments as those described above might be performed to discover links between genetic traits (snips for example) and pain evolution or pain treatments efficacy.

10.1.2. DETERMINATION OF SAMPLE SIZE

The determination of the sample size is presented in Section 4.2.1.

10.1.3. STUDY PARTICIPANT DISPOSITION

All patients who discontinue from the study will be identified, and the extent of their participation in the study will be reported. If known, a reason for their discontinuation will be given.

10.1.4. STUDY PARTICIPANT CHARACTERISTICS

The patient's age, sex or other demographic characteristics will be recorded and may be used in the pharmacodynamic analyses as quantitative or classification variables.

10.1.5. STATISTICAL EVALUATION OF SYMPTOMS

All prescribed analgesic treatment, analgesic rescue medication and symptoms related to pain treatment will be listed, and if the frequency of symptoms allows, they will be summarized using descriptive procedure.

The incidence of symptoms will be presented by severity and by association with class of analgesic treatment.

Where changes in severity are recorded in the CRF, the most severe incidence of the symptom will be reported in the tables and listings. A baseline sign and symptom is defined as a symptom that starts after the enrolment of patient.

The frequency (the number of symptoms, the number of patients experiencing a symptom and the percentage of patients experiencing a symptom) of symptoms will be summarized by class of treatment, MedDRA system organ class and preferred term. Any severe and/or serious symptom will be tabulated.

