4.1.1. SCREENING AND ENROLMENT VISIT

FIRST CASE SCENARIO: SCREENING AND ENROLMENT AT VISIT 1

In this case scenario, all Visit 1 assessments are performed during only one visit, this visit will take place as described below.

First, the study purpose – including the optional genotyping research study - will be explained to patients who will then sign and date the Informed Consent Document (ICD) before completing any study procedure. In addition, patients who consent to take part in the genotyping exploratory research will also sign a specific genotyping ICD to allow the use of their archived tumor tissue block, if any and/or of an aliquot of standard safety laboratory blood sample.

Patients' WAPS will be collected and a value of at least 4 will be required to take part in the study. Patients' standard demographic, relevant medical and primary disease history, primary disease treatment history, analgesic treatment history up to one month prior to entry into the study, symptoms related to analgesic treatment, if any as well as cancer concomitant therapies will then be recorded. Patients will also undergo an abbreviated physical examination.

[figure not shown]
After checking completion of all inclusion/exclusion criteria, eligible patients will be enrolled in the study and perform the baseline Clinical Pain Assessments (CPAs). The following questionnaires will also be completed: pain disease questionnaires (DN4, NPSI and PCS), Brief Pain Inventory (BPI) questionnaire, expectation questionnaire, personality traits questionnaires (MHLCS, HADS and LOT-R) and quality of life questionnaire (Quality-of-Life Questionnaire in 30 questions (QLQ-C30)). The PGAC and IGAC will be completed by the patient and the Investigator, respectively.

At the end of the Visit and after patient evaluation, the Investigator will initiate or review as necessary the analgesic treatment and the patients will enter an observational period of approximately 4 weeks.

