5. POPULATION RECRUITMENT, ENROLMENT AND WITHDRAWAL

5.1. DEFINITIONS

Screening Failure:

A patient is considered as a screening failure when he/she is screened but not enrolled in the study as not meeting eligibility criteria.

Patient Enrolment:

A patient is considered as enrolled in the study when he/she meets all eligibility criteria and he/she performs CPAs at Visit 1 or Visit 1A.

Patient Dropout:

A patient will be considered as dropout when, for any reason, he/she withdraws from the study or is discontinued from the study prior to study completion.

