8.3.1. SYMPTOMS MONITORING

Definition of Adverse Event (AE)

Typically, a clinical study AE is any untoward medical occurrence in a patient or clinical study patient administered an investigational medicinal product and which does not necessarily have a causal relationship with this treatment.

This does not apply to this observational study. Nevertheless the symptoms related to analgesic treatment(s) will be collected.

Symptoms Collection and Reporting

At enrolment, study site personnel will record the occurrence, time of onset, nature and severity of symptoms related to analgesic treatment. Up to Visit 2, site personnel will record any change in the occurrence and nature of symptoms related to analgesic treatment or having an impact on pain evaluation. The nature, time of onset, duration, severity will be documented and each symptom will be classified by the most suitable term from a version of a Medical Dictionary for Regulatory Activities (MedDRA) agreed by the Sponsor and other parties involved in the study.

The condition of each patient will be monitored throughout the study. In addition, any sign or symptom related to pain treatment will be observed and elicited at least at each visit by open questioning, such as “How have you been feeling since you were last asked?”

Patients will also be encouraged to report spontaneously any symptom occurring at any other time during the study.

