16.2. ATTACHMENT 2 – STUDY SCHEDULE – ENROLMENT AND SCREENING AT VISIT 1A

Visit	Screening Enrolment		Observational Period		Follow UP / Early Discontinuation Phone Call
	1A	1B	Optional Intermediate Evaluation ^f	2	
Days	Day 1	Day 8 (+ 21 days)	Visit 1B Day + 14 days (+ 12 to + 18 days)	Visit 1B Day + 28 days (+ 14 days)	7 days after Visit 2 (+ 7 days)
Informed Consent (general and genotyping) ^a	X				
Demographics	X				
Abbreviated physical examination	X			X	
Primary disease and Relevant Medical History	X				
Primary disease treatment history	X				
Analgesic history (within 1 month before enrolment)	X				
Pre-existing Conditions/Symptoms related to pain treatment	X	X	X	X	X
Cancer Concomitant Medications	X	X	X	X	X
Inclusion/Exclusion Criteria	X				
Enrolment into study	X				
Clinical Pain Assessments ^d	X		X	X	
DN4, NPSI	X				
Expectation questionnaire	X				
QLQ-C30	X			X	
BPI (short form)	X		X	X	
IGAC and PGAC	X			X	
APS and WPS ^e	X			X	X
Laboratory analysis ^b					
Aliquot of blood sample for genotyping purpose ^a					
Diary completion					
Compliance to diary completion		X	X	X	

Compliance to prescribed analgesic treatment ^c		X	X	X	
Analgesic treatment review	←—————→				
Questionnaires MHLCS, HADS, LOT-R, PCS		X			

Abbreviations:

APS = Average pain score; BPI = Brief Pain Inventory; DMA = dynamic mechanical allodynia; DN4= Douleur Neuropathique en 4 questions; HADS = Hospital Anxiety and Depression Scale; IGAC=Investigator Global Assessment of Changes; LOT-R = Revised Life Orientation Test; MHLCS = Multidimensional Health Locus of Control Scale; MPT= mechanical pain threshold; NPSI= Neuropathic Pain Symptom Inventory; MPA = Most Painful Area; PCS= Pain Catastrophizing Scale; PGAC= Patient Global Assessment of Changes; QLQ-C30=quality-of-life questionnaire in 30 questions; SA= static allodynia; TPS= thermal pain sensitivity; WPS = Worst pain score.

- ^a Aliquot of standard safety laboratory blood sample for genotyping is optional in this study (will be performed if patient gives his consent by signing the genotyping informed consent document). The aliquot can be taken at any time during the study.

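### Protocol section 10.1.5 defines a baseline symptom as one starting after enrolment, which contradicts the protocol's own use of baseline and leaves pre-existing symptoms without a category

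*Protocol*

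**What the plan says.** Protocol section 10.1.5 plans the symptom summaries. Symptoms are listed and, if frequent enough, summarised descriptively. On incidence it says: "The incidence of symptoms will be presented by severity and by association with class of analgesic treatment". Frequencies are also tabulated by treatment class and by MedDRA grouping, and severe or serious symptoms are tabulated as well. Where severity changed, the worst recorded grade is reported. In the middle of these rules stands the definition: "A baseline sign and symptom is defined as a symptom that starts after the enrolment of patient".

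Section 8.3.1 governs collection, in two steps. First: "At enrolment, study site personnel will record the occurrence, time of onset, nature and severity of symptoms related to analgesic treatment". Then: "Up to Visit 2, site personnel will record any change in the occurrence and nature of symptoms related to analgesic treatment".

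The SAP introduction leaves safety analyses on the complete database to the sponsor, for the Clinical Study Report. The SAP does not define a baseline symptom, and its list of changes from the protocol (section 1.2) does not mention the subject. The protocol's amendment summary has an entry for section 10.1.5, but it does not touch this sentence. The definition is therefore current text, and it is the only one in the documents.

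**The concern.** A baseline label normally separates what patients brought into the study from what arose during it. Here it is attached to the second group. Patients enter because their pain relief is unsatisfactory, and section 6.3 records analgesics taken in the preceding month. Some can therefore be expected to arrive with symptoms caused by earlier analgesic treatment. Unless these are kept apart from symptoms that begin after the enrolment visit, incidence by analgesic class cannot be read as describing treatment during the observation period.

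The one sentence that could separate the two groups labels them the wrong way round. Whoever programs the sponsor's tables has no other rule in the documents to follow.

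**Working it through.** No arithmetic applies: the point concerns a definition, and the plan gives no symptom rate to reproduce. The check is to set the definition beside the other sections that fix enrolment, baseline, symptom recording and the start of observed treatment.

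1. **When enrolment occurs.** Section 5.1: "A patient is considered as enrolled in the study when he/she meets all eligibility criteria and he/she performs CPAs". That is at Visit 1 or Visit 1A, which Tables 1 and 2 in section 8.5.4 call Day 1.
2. **What baseline means elsewhere.** Section 4.1.1 says of Visit 1: "eligible patients will be enrolled in the study and perform the baseline Clinical Pain Assessments (CPAs". The baseline pain assessments thus belong to the enrolment visit and do not come after it.
3. **When observed treatment starts.** Section 4.1.1, at the end of that visit: "the Investigator will initiate or review as necessary the analgesic treatment and the patients will enter an observational period". A symptom starting after the visit therefore arises under the treatment being observed.
4. **What is recorded about symptoms.** Under section 8.3.1, symptoms existing at enrolment are recorded with time of onset, and later changes are recorded up to Visit 2. The matching row in Attachment 2 is headed "Pre-existing Conditions/Symptoms related to pain treatment" and is marked from Visit 1A through the follow-up call. Collection thus begins with pre-existing symptoms at the enrolment visit.

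Applying the two usages to the possible cases:

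| Symptom | Under section 10.1.5 as written | Under the usage in sections 4.1.1 and 8.3.1 |
|---|---|---|
| Started before Day 1, present at enrolment | Not baseline; no category given | Baseline |
| Started after enrolment, by Visit 2 | Baseline | Arises during observation |
| Present at enrolment, more severe later | Not baseline; no category given | Baseline, with a later change |

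The first two rows are reversed. The protocol has no named category for symptoms that are not baseline, so as written the first and third rows are unclassified.

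5. **Which outputs use the label.** None of the tables described in section 10.1.5 is split by, restricted to, or net of baseline symptoms. Read literally, they count every recorded symptom, whether it began before or after enrolment.
6. **Which other analyses use it.** The primary endpoint is the change in weekly mean APS (section 2.2). The secondary endpoints are pain, global assessment and quality-of-life measures. The patient variables in SAP section 4.2 include no symptom variable, and the SAP's models predict APS-based outcomes. None of these depends on the definition.

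**The case against.** The strongest reply is that the sentence changes no planned number. A reader might infer that the by-class tables would attribute pre-existing symptoms to the study-period analgesics because of the reversed rule, that new symptoms would be hidden, or that every symptom would be misclassified. The documents do not support this. The tables do not use the label, so nothing is hidden by it. If pre-existing symptoms enter the incidence figures, the cause is that no split is planned. It would also be wrong to call incidence by class the study's only tolerability output, since listings and the severe or serious tabulation are planned too, and section 8.3.2 collects SAE-related withdrawals. The synopsis says that safety data are not collected as such.

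A second reply is that the sentence may have been meant to say which symptoms are counted, with baseline simply the wrong word. It stands between the severity rule and the frequency rule, so this is possible. On that reading the intended set would be post-enrolment symptoms, which is the sensible one.

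A third is that onset times are recorded, so the error can be repaired at reporting.

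All three replies limit the consequence, but none makes the sentence correct. On either reading a word or a rule is wrong, and the documents do not say which. If the label is never used, old and new symptoms are pooled in the incidence by class, which is the other half of the same gap. That the error can be repaired later is a reason to correct it cheaply now, since otherwise the programmer has to guess the intent.

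**Conclusion.** The definition in section 10.1.5 is wrong as written and conflicts with sections 4.1.1 and 8.3.1 and Attachment 2. Wherever the label is applied, symptoms arising under observed treatment are called baseline and pre-existing symptoms are left without a category. Where it is not applied, the by-class incidence mixes the two.

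The effect is confined to descriptive symptom summaries. How many symptoms are involved cannot be estimated, because the documents give no rates of symptoms before or after enrolment. The conclusion rests on two assumptions: that baseline should mean for symptoms what it means for the pain assessments, and that the sponsor's safety reporting will follow section 10.1.5, since the SAP offers no alternative.

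**What to change.** Replace the sentence in section 10.1.5 with two definitions:

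- A baseline symptom is one present at enrolment or starting before it.
- An on-study symptom is one starting after enrolment, or one present at enrolment for which the CRF records an increase in severity afterwards.

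Then state that incidence by analgesic class, by severity and by MedDRA grouping is presented for on-study symptoms, with baseline symptoms tabulated or listed separately. For symptoms starting on Day 1, use the recorded time of onset, and treat those noted at the enrolment visit as baseline.

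The cost is a few sentences and one extra split in the table shells. Time of onset is already collected under section 8.3.1, and section 10.1.5 already foresees severity changes in the CRF. The sponsor should confirm that the CRF shows at which visit a severity change was recorded, because the worsening part of the definition depends on it and section 8.3.1 does not say so. Section 10.1.1 expects the SAP to cover safety variables and to be final before database lock. The corrected definition can therefore be placed there, or in the sponsor's plan for the safety analyses, with the protocol sentence aligned at the next amendment.
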